| 1.Research Personnel Costs (For related insurance premiums, please consult the Human Resources Department) | 
(1) Full-time Personnel (for individual project applications only):
 
 • Work remuneration (including year-end bonus reserve) • Employer contribution to labor and health insurance • Employer contribution to labor pension (6% of insured salary) 
(2) Part-time Personnel (must be enrolled students):
 
 • Work remuneration 
  Undergraduate student  Master's student  Other: • Employer contribution to labor and health insurance • Employer contribution to labor pension (6% of insured salary) 
(3) Temporary Workers:
 
 • Work remuneration • Employer contribution to labor and health insurance • Employer contribution to labor pension (6% of insured salary) | | | | |
| 1. Operational Expenses | (4) Professional Assistance Fees | 12,000 | 40 | 480,000 | |
| | | | Subtotal: | 480,000 | |
| 2.Animal Experimentation Fees | | | Subtotal: | | |
| 3.Consumables, Equipment, Books, and Miscellaneous Expenses | Participant Stipends Miscellaneous: Postage and Telecommunications, Printing Costs, Copy Paper, Copying | 500 1,000 15,000 | 210 40 1 | 105,000 40,000 15,000 | |

| | | | | | |
|---|--|--|-----------|----------------|--|
| | Fees, Binding Fees, Stationery Costs, Poster Production Fees, Computer Data Statistics Fees, Computer Data Analysis Fees, Paper Submission Fees, Paper Publication Fees, Sectioning, Embedding, and Staining Immunology Costs. | | | | |
| | | | Subtotal: | 160,000 | |
| 2. Research Equipment Costs (According to regulations, books, computers, and peripheral equipment are not included in the subsidy. Medium and large instruments will be applied for collectively by the research department, based on necessity, for shared use.) | | | Subtotal: | 0 | |
| | Total | | | 640,000 | |

6. Project Abstract

(Please provide a summary of the key points of this project within 500 words, and create customized keywords based on the nature of the project.)

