Previous research has shown that neuromodulators can effectively reduce symptoms in patients with irritable bowel syndrome (IBS) or functional dyspepsia by modulating visceral hypersensitivity through central and peripheral mechanisms.^{35,36} Therefore, using neuromodulators to regulate visceral hypersensitivity and esophageal hypervigilance in esophageal brain-gut axis communication disorders is considered a feasible strategy. However, a systematic review of the literature shows that among the few available randomized controlled trials, the efficacy of neuromodulators in the various subtypes of esophageal brain-gut axis communication disorders is inconsistent.³⁷ Therefore, whether neuromodulators can be widely used in the treatment of these disorders still requires more supporting evidence.

Cognitive Behavioral Therapy (CBT) is a form of psychological treatment that functions as a brain-gut axis intervention. It can modify the pain perception pathways of the brain-gut axis, reduce hypervigilance and symptom-specific anxiety, and is considered effective in improving chronic esophageal symptoms associated with disorders of brain-gut axis communication.

This approach includes the measurement of Heart Rate Variability (HRV), which involves collecting raw electrocardiogram signals through a biofeedback system or using photoplethysmography (PPG) sensors to detect pulse wave signals. These signals are then converted into HRV indicators, which serve as markers of autonomic nervous system activity.

Heart Rate Variability Biofeedback (HRVB) can enhance HRV indices and has been shown to be effective in individuals with physical illnesses, psychological disorders, and even in healthy populations.^{38, 39}

Recent studies have shown that Cognitive Behavioral Therapy (CBT) can improve esophageal symptoms and quality of life in individuals with supragastric belching and non-erosive reflux disease (NERD).⁴⁰⁻⁴² Currently, Cognitive Behavioral Therapy (CBT) for gastrointestinal disorders typically involves 6 to 8 therapy sessions. In this study, participants will undergo either six weeks of CBT or lifestyle management, administered by psychologists trained in CBT and conducted in accordance with the clinical guidelines of the American Gastroenterological Association (AGA).⁴³

[figure not shown]

Figure 2. The primary goal of Cognitive Behavioral Therapy (CBT) is to modify maladaptive thoughts and behaviors in order to reduce esophageal hypervigilance.

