Research Objectives

The objectives of this study :

Exploring the Effects of Cognitive Behavioral Therapy on Disorders of Esophageal Brain-Gut Axis Dysregulation.

Hypothesis:

- (1) Patients with disorders of esophageal brain-gut axis dysregulation often experience esophageal symptoms due to visceral hypersensitivity and esophageal hypervigilance, which can negatively affect their physical and mental health, sleep, and quality of life. Cognitive Behavioral Therapy (CBT) can help alleviate these symptoms and reduce their impact.
- (2) CBT has been shown to improve symptoms across different subtypes of disorders involving esophageal brain-gut axis dysregulation.

8. Research Methods, Procedures, and Execution Progress

1. Please describe in detail the research methods adopted in this project and the reasons for choosing them.
2. Potential challenges and solutions expected during the project.
3. If this is a continuous project, please also attach the progress report from the previous year or primary data.

Research Method

Participant

This project is a multi -center study. we will recruit cases from three medical centers in Taiwan, We plan to enroll a total of 120 participants, including 40 from our hospital, 40 from Kaohsiung Medical University Hospital, and 40 from E-Da Hospital.

This study is expected to last for 2 years, with the study period ending on December 31, 2025. We intend to recruit participants with esophageal symptoms related to disorders of the gut-brain axis communication from the Gastroenterology outpatient clinics.

Inclusion criteria for participants :

1. Age between 18 and 75 years, with clear consciousness and willingness to sign the informed consent form.

[figure not shown]
Version Date : (Version 8, 11/19/2024)

2. Participants with chronic esophageal symptoms related to esophageal-brain-gut axis communication disorders (such as heartburn, acid reflux, sensation of a foreign body in the throat, difficulty swallowing, chest pain, and chest tightness).

Exclusion criteria for participants :

1. Esophageal stricture, or a history of esophageal, gastrointestinal, or throat surgery.
2. Structural esophageal diseases (e.g., diverticula, esophageal rings), infectious esophagitis, erosive esophagitis, eosinophilic esophagitis.
3. Non-erosive gastroesophageal reflux disease or significant esophageal motility disorders.
4. A history or current diagnosis of esophageal, gastrointestinal, or other organ malignancies.

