5. Significant endocrine or rheumatic autoimmune diseases that may affect gastrointestinal motility.
6. Continuous use of medications that may affect esophageal motility (e.g., anticholinergics, morphine-like drugs, nitrates, calcium channel blockers) within the past month.
7. Use of antidepressants, selective serotonin reuptake inhibitors, or other psychiatric medications within the past three months.
8. Pregnant or breastfeeding women.
9. Individuals with mental disorders or those unable to cooperate.
10. Known allergy to tricyclic antidepressants.
11. Known allergy to selective serotonin reuptake inhibitors.
12. Known allergy to any component of proton pump inhibitors.

Research Design Flowchart

Steps to Follow

In this study, All participants will undergo questionnaire assessments and heart rate variability measurements before treatment. The questionnaires include the Gastroesophageal Reflux Disease Questionnaire (GERDQ), PROMIS GERD, DSI & GSS, RSI, Brief Esophageal Dysphagia Questionnaire (BEDQ), Esophageal Hypervigilance and Anxiety Scale (EHAS), Visceral Sensitivity Index (VSI), Sleep and Mental Health Questionnaires (Sleep Habits Questionnaire PSQI, Taiwanese Depression Questionnaire TDQ, State-Trait Anxiety Inventory STAI, Functional Dyspepsia (FD) Questionnaire, Irritable Bowel Syndrome (IBS) Questionnaire, Quality of Life Questionnaire SF-12, and Northwest Esophageal Quality of Life Scale (NEQOL). Heart rate variability will be measured using the non-invasive "Mind Technology" biofeedback system (Taiwan FDA Medical Device Certification No. 011374).

Following this, a single-blind trial will be conducted with computer-generated random allocation. Participants will receive either 6 weeks of Cognitive Behavioral Therapy (CBT) or 6 weeks of lifestyle management (sham control), with one 1-hour session per week. After 6 weeks of counseling, participants will undergo a final questionnaire assessment and heart rate variability measurement after the 12th week of enrollment. The questionnaires and measurements will take approximately 20 to 30 minutes to complete, marking the end of the trial.

Cognitive Behavioral Therapy (CBT) will be carried out according to the following steps :

(1) Education and Initial Follow-up

Version Date : (Version 8, 11/19/2024)

- (2) Heart Rate Variability and Breathing Introduction
- (3) Cognitive Restructuring and Breathing Application
- (4) Cognitive Diffusion and Behavioral Experiments

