- (5) Problem-Solving and Emotion-Focused Coping Strategies
- (6) End of Treatment and Relapse Prevention

Lifestyle Management (Sham Control) will be carried out according to the following steps :

- (1) Education and Initial Follow-up
- (2) Dietary Habits: What, When, Where, Why
- (3) Changing My Diet: Strategies and Barriers
- (4) Lifestyle Factors: Alcohol, Smoking, and Sugar
- (5) Lifestyle Factors: Sleep and Exercise
- (6) End of Treatment and Relapse Prevention

In this study, we will use non-invasive physiological signal sensors connected to a biofeedback system to measure the participants' physiological signals, including electrocardiogram (ECG) and breathing. Before measurement, participants will first apply ECG electrodes for a two-lead ECG measurement, which will then be converted into heart rate variability (HRV) indicators. Simultaneously, a non-invasive breathing sensor will be used to measure the respiratory rate per minute. Except for a very small number of participants who may experience allergic reactions to the ECG electrodes, the likelihood of side effects is less than 1%.

Multicenter Communication and Coordination Method

The hospital directors of the participating institutions and the principal investigator, [name], will communicate and coordinate via email and a Line group established for the project. The research data collected by each center will be managed and stored by the respective center's director. The hospital directors will assist in consolidating the research data from their institution, and the electronic data will be coded for identification. After the data is compiled, it will be sent back to the principal investigator. Additionally, the research physicians and staff at each participating center will have regular video conferences (every 2 months) to discuss and report on the progress of the study.

Statistical Analysis

All data will undergo normality testing using the Kolmogorov-Smirnov test. If continuous variables follow a normal distribution, they will be expressed as means and standard deviations; if not, they will be presented as medians and interquartile ranges.

For categorical variables, the Chi-square test or Fisher's exact test will be used for analysis. Continuous variables that are normally distributed will be analyzed using the unpaired t-test, while non-normally distributed continuous variables will be analyzed using the Mann-Whitney U test.

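### The two-sample tests fixed in the protocol have no centre or therapist term, and they can reject too often if each psychologist delivers only one arm

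*Protocol*

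**What the plan says.** Delivery is described in the Background (section 7, treatment strategies): "participants will undergo either six weeks of CBT or lifestyle management, administered by psychologists trained in CBT". Under Steps to Follow (section 8), each arm runs for six weeks "with one 1-hour session per week", after "computer-generated random allocation". No allocation ratio or stratification factor is given.

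Under Participant (section 8), "We plan to enroll a total of 120 participants", 40 at each of three hospitals.

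The Statistical Analysis section fixes the comparisons. "Continuous variables that are normally distributed will be analyzed using the unpaired t-test", non-normal continuous outcomes go to the Mann-Whitney U test, and categorical outcomes go to a chi-square or Fisher's exact test. ANOVA or Kruskal-Wallis is kept for larger numbers of groups. The threshold is p < 0.05. None of these analyses has a term for centre or therapist.

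The protocol does not state how many psychologists there are, or whether each delivers CBT, lifestyle management or both.

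**The concern.** Randomising individuals makes the arms comparable at baseline. It does not make outcomes independent after treatment, because patients seen by the same psychologist share that person's skill and manner.

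If each psychologist delivers only one arm, differences between psychologists are confounded with the difference between treatments. The unpaired t-test then estimates its standard error from patient-to-patient variation and understates the uncertainty. An apparent benefit of CBT could reflect one or two good therapists rather than the therapy. The protocol intends its results to establish a CBT model and to guide treatment, so that distinction matters.

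The described data flow does not mention recording who treated whom. If this is not recorded, it may be hard to reconstruct later.

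**Working it through.** **From the protocol:** N = 120, three centres of 40, psychologist delivery in both arms, unpaired t-test, threshold 0.05.

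**Assumed, because not stated:** two-sided testing, 1:1 allocation (60 per arm), number of therapists, and therapist ICC, taken from 0 to 0.10. Outcomes are scaled to a total variance of 1.

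**The plan's own figure.** The protocol gives no effect size, SD or power behind 120, so that number cannot be reproduced. For reference, 60 per arm gives 80% power at (1.960 + 0.842) × √(2/60) = 0.51 SD if patients are independent.

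**Case A: each psychologist delivers one arm.** Take three therapists per arm with m = 20 patients each.
- Design effect: DE = 1 + (m − 1) × ICC = 1 + 19 × ICC.
- Actual type I error of the nominal 5% test: 2 × [1 − Φ(1.96/√DE)].
- Effective total N: 120/DE.

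| ICC | DE | √DE | Effective N | Type I error, formula | Type I error, simulated |
|---|---|---|---|---|---|
| 0 | 1.00 | 1.00 | 120 | 0.050 | 0.051 |
| 0.01 | 1.19 | 1.09 | 101 | 0.072 | 0.072 |
| 0.05 | 1.95 | 1.40 | 62 | 0.160 | 0.161 |
| 0.10 | 2.90 | 1.70 | 41 | 0.250 | 0.255 |

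The simulation applied the unpaired t-test to 40,000 trials per setting. The assumed caseload matters. By the same formula, 10 patients per therapist gives about 6%, 10% and 16% at ICC 0.01, 0.05 and 0.10, and one therapist per arm (60 each) gives about 12%, 32% and 46%.

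**Case B: psychologists deliver both arms.** This was simulated with one therapist per centre.
- *Allocation balanced within therapist.* The therapist effect cancels from the difference, whose true SE is √[2(1 − ICC)/60]. At ICC 0.10 this is 0.173, while the t-test's average SE is 0.179. Simulated type I error is 4.8%, 4.5% and 4.4% at ICC 0.01, 0.05 and 0.10.
- *Allocation not stratified.* Simulated type I error is 4.9%, 5.0% and 5.0%. The test is valid.
- *Balanced, but therapists differ in how well they deliver each arm.* Take a variance of 0.02 for each therapist-and-arm combination and ICC 0. The true SE is √(2 × 0.98/60 + 2 × 0.02/3) = 0.214, against a t-test SE of 0.182. Simulated type I error is 9.7%, and it stays at about 9% to 10% across the ICC range.

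**Centre.** Patients are randomised individually and each centre is expected to contribute to both arms. Leaving centre out puts between-centre variation into the error term. That costs precision, or makes the test slightly conservative if allocation is stratified, but it does not inflate type I error.

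**Cost of a therapist random effect in Case A.** Six therapists leave 6 − 2 = 4 degrees of freedom, so the critical value is 2.776 instead of 1.980. The interval is √DE × 2.776/1.980 times as wide as the t-test's, which is 1.5, 2.0 and 2.4 at ICC 0.01, 0.05 and 0.10. The difference detectable with 80% power rises from 0.51 SD to about 0.75, 0.96 and 1.17 SD.

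**The case against.** The strongest reply is that the large error rates belong to a scenario the protocol never describes. It names a single pool, "administered by psychologists trained in CBT", for both interventions, so psychologists working in both arms is at least as natural a reading. On that reading the t-test holds its level or is slightly conservative. The therapist count and the ICC are assumptions, and at ICC zero nothing is wrong. All of this stands, and it makes the concern conditional. It does not remove it, because the protocol does not rule out arm-specific psychologists, and sharing psychologists across arms is safe only if they deliver both equally well.

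Two stronger readings are not supported:
- *That patients are treated in groups.* No group format is stated. The budget lists professional assistance fees at 12,000 × 40 = 480,000, and 40 is one centre's patient count. That hints at a per-patient fee, though only by inference. The clustering at issue comes from sharing a therapist.
- *That the standard error is wrong however therapists are assigned.* Case B shows otherwise.

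It may also be said that block structure, data fields and ICC reporting belong in an analysis or randomisation plan. That is fair for the details, and the protocol does not say that therapist identity will go unrecorded. But it does name the tests, and those tests have no centre or therapist term.

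**Conclusion.** The point holds conditionally. For a trial delivered by psychologists at three centres, the protocol fixes tests that assume independent patients, and it omits the fact needed to judge them: whether each psychologist delivers one arm or both.

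The nominal 5% test may be sound or slightly conservative (about 4.4% to 5%). It may also reject a true null about 7% to 25% of the time, if therapists are arm-specific with 20 patients each and the ICC is 0.01 to 0.10. The documents do not show which applies, so they do not establish that the type I error is inflated. Omitting centre is a loss of precision only.

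The case for change rests mainly on its low cost: a better allocation and model are available for very little. The random-effect model for arm-specific therapists is a real trade-off, because it gives up much power, and the recommendation does not depend on it.

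**What to change.** 1. State how many psychologists there are at each centre and whether each delivers one arm or both.
2. Run the computer-generated allocation in permuted blocks within centre, and have each centre's psychologists deliver both arms where feasible.
3. Record the treating psychologist for every participant.
4. Replace the unpaired test of continuous outcomes with a linear model containing arm and centre, or arm and therapist as a fixed factor when psychologists deliver both arms.
5. If psychologists must be arm-specific, add a sensitivity analysis with a therapist random effect and small-sample degrees of freedom. State in advance that with about six therapists its interval would be roughly 1.5 to 2.4 times as wide as the t-test's.

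The cost of items 1 to 4 is one data field, a stratified list, revised wording and a few degrees of freedom. No extra patients are needed and the content of the treatments does not change. A fixed therapist factor does not correct for psychologists who deliver the two arms unequally well. Recording therapist identity at least lets that variation be examined, though imprecisely with few therapists.

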Gastroesophageal reflux disease (GERD) poses a challenging medical condition to manage, with up to 40% of patients showing refractory to standard medical intervention, which usually begins with a proton pump inhibitor (PPI). Among these cases, esophageal disorders of gut-brain interaction (DGBI), such as reflux hypersensitivity and functional heartburn, or GERD patients with concurrent occurrences of these conditions, constitute more than 90% of the patients who did not respond to twice-daily PPI treatment. Esophageal visceral hypersensitivity and hypervigilance are the two pathways that drive esophageal DGBI and symptoms. The Rome IV esophageal disorders, encompassing functional chest pain, functional heartburn, globus, functional dysphagia, and reflux hypersensitivity, are defined by present with symptoms originating from the esophagus without detectable evidence of structural, inflammatory, or motor disorders. Diagnosing esophageal DGBI necessitates testing involving endoscopy, pH-impedance monitoring, and high-resolution manometry. Neuromodulators form the basis of the pharmacological strategy for managing various esophageal DGBI and symptoms, modulating both peripheral and central hyperalgesia. Increasing evidence supports the use of brain-gut behavioral therapies, such as gut-directed hypnotherapy and cognitive behavior therapy, as effective treatments for a variety of DGBIs. However, the efficacy of neuromodulators or cognitive behavior therapy in treating esophageal DGBI and related symptoms remains largely unexplored. The primary objective of this study is to examine the efficacy of cognitive behavior therapy in managing esophageal DGBI. Additionally. The findings from this study will contribute to a better understanding of the pathophysiology of esophageal DGBI and GERD with refractory symptoms. These clinical insights may then offer valuable guidance for future therapeutic approaches in DGBI patients who experience esophageal symptoms and do not respond to PPI treatment.

Key words: gastroesophageal reflux disease, disorders of gut-brain interaction, neuromodulators, cognitive behavior therapy

7. Background and Objectives of the Research Project

(Please provide a detailed description of the background, objectives, significance of this research project, as well as the research status both domestically and internationally related to this project. Also, include a review of important references and literature.)

Research Background

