For comparisons involving more than three groups, if the data are normally distributed, an ANOVA with post hoc tests will be conducted. If the data are non-normally distributed, the Kruskal-Wallis test will be applied. A p-value of less than 0.05 will be considered statistically significant.

Statistical analyses will be performed using SPSS 19 for Windows (SPSS, Inc., Chicago, IL, USA).

Clinical Significance and Originality of This Study

1. The originality of this study lies in its use of visceral sensitivity, mind-body connection, esophageal hypersensitivity, anxiety questionnaires, and functional gastrointestinal questionnaires to explore the effects of neuromodulators on diseases related to esophageal-brain-gut axis communication abnormalities. Patients with such conditions often experience more severe esophageal symptoms due to excessive visceral sensitivity and esophageal hypersensitivity.
2. This study aims to establish a model for Cognitive Behavioral Therapy (CBT) in disorders of esophageal brain-gut axis dysregulation. Our research examines the role of CBT in esophageal brain-gut axis dysregulation and refractory gastroesophageal reflux disease (GERD). The results obtained from this study will deepen our understanding of the pathophysiological mechanisms of esophageal brain-gut axis dysregulation and refractory GERD. The findings will help elucidate the etiology of refractory GERD, particularly when patients with GERD also present with esophageal brain-gut axis dysregulation, which leads to a lowered threshold for esophageal symptom perception. This condition can be reversed and improved through the aforementioned treatments. Furthermore, it will assist in early clinical intervention for patients with brain-gut axis communication disorders, enabling the establishment of personalized treatment strategies and the achievement of precision medicine for such patients.

9.Expected Work Items and Specific Outcomes

- (1) Please list the expected tasks to be completed within the execution period.
- (2) Expected contributions to academic research and other applied areas.
- (3) Expected training that participants will receive.

(1) Work items expected to be completed.

In this study, we will also explore the effects of Cognitive Behavioral Therapy (CBT) on disorders of esophageal brain-gut axis dysregulation, as well as its impact on physical and mental health and quality of life.

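### The protocol's efficacy objective has no primary outcome: 14 or 15 questionnaires plus heart rate variability share one unranked p < 0.05 rule

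*Protocol*

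**What the plan says.** The Project Abstract (section 6) sets the aim: "The primary objective of this study is to examine the efficacy of cognitive behavior therapy in managing esophageal DGBI". The Research Objectives in section 7 put it more loosely: "Exploring the Effects of Cognitive Behavioral Therapy on Disorders of Esophageal Brain-Gut Axis Dysregulation".

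Two hypotheses follow. The first describes effects of these disorders on symptoms, physical and mental health, sleep and quality of life, and then says "Cognitive Behavioral Therapy (CBT) can help alleviate these symptoms and reduce their impact". The second reads "CBT has been shown to improve symptoms across different subtypes of disorders involving esophageal brain-gut axis dysregulation". Neither names an instrument.

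Section 8, Steps to Follow, lists the pre-treatment assessments. The list begins "The questionnaires include the Gastroesophageal Reflux Disease Questionnaire (GERDQ), PROMIS GERD, DSI & GSS, RSI, Brief Esophageal Dysphagia Questionnaire (BEDQ" and goes on to EHAS, VSI, PSQI, TDQ, STAI, the functional dyspepsia and IBS questionnaires, SF-12 and NEQOL; HRV is measured as well. After treatment, "participants will undergo a final questionnaire assessment and heart rate variability measurement after the 12th week of enrollment". No measure is called primary, secondary or key.

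The Statistical Analysis section chooses between the t-test and the Mann-Whitney test for each continuous variable by a Kolmogorov-Smirnov normality test, and ends with one criterion: "A p-value of less than 0.05 will be considered statistically significant".

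**The concern.** A primary objective of efficacy needs a variable that decides it. The protocol fixes the tests and the significance level but not the variable they are to decide on. If one scale out of many is significant, a reader cannot tell a real effect on an outcome chosen in advance from a scale picked after the results were seen.

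The sample size does not reveal an intended outcome either. The 120 participants (40 at each of three centers) come with no effect size, standard deviation or power in the text available.

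An analysis plan that is not shown may well handle multiplicity adjustment. Which outcome answers the primary objective is a choice for the protocol, and this protocol has its own statistics section that leaves it open.

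**Working it through.** **No figure to reproduce.** The protocol gives no power or error-rate calculation. The only figure that can be checked is enrollment: 40 + 40 + 40 = 120, which agrees.

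**Inputs from the protocol**
- Significance level: 0.05 (Statistical Analysis). Sidedness is not stated.
- Questionnaires (Steps to Follow): GERDQ, PROMIS GERD, DSI & GSS, RSI, BEDQ, EHAS, VSI, PSQI, TDQ, STAI, FD, IBS, SF-12, NEQOL. That is 14, or 15 if DSI and GSS are two instruments.
- HRV: indicators in the plural, number not given. Counted here as one, which is a minimum.

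**Assumptions**
- Two-sided tests, critical value 1.96, and one test per outcome.
- No true effect of CBT on any outcome.
- Test statistics equally correlated at r. No correlation is given, so r runs from 0 to 0.9. Zero is an upper bound and unlikely for scales completed by the same patients.

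**Families of outcomes**
- k = 5 or 6: GERDQ, PROMIS GERD, DSI & GSS as one or two, RSI and BEDQ, assumed to be symptom scores.
- k = 12: all questionnaires except FD and IBS, with DSI & GSS as one and no HRV.
- k = 16: all questionnaires with DSI & GSS as two, plus HRV as one.

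**Formulas.** With φ and Φ the standard normal density and distribution function, and a shared component c:
- Favouring CBT: P = 1 − ∫ Φ((1.96 − √r·c)/√(1−r))^k φ(c) dc.
- Either direction: P = 1 − ∫ [Φ((1.96 − √r·c)/√(1−r)) − Φ((−1.96 − √r·c)/√(1−r))]^k φ(c) dc.
- At r = 0 these reduce to 1 − 0.975^k and 1 − 0.95^k. For example, 1 − 0.975^6 = 0.141, 1 − 0.975^16 = 0.333 and 1 − 0.95^16 = 0.560.

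**Chance of at least one false result favouring CBT**

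| k | r = 0 | r = 0.3 | r = 0.5 | r = 0.7 | r = 0.9 |
|---|---|---|---|---|---|
| 1 | 0.025 | 0.025 | 0.025 | 0.025 | 0.025 |
| 5 | 0.119 | 0.105 | 0.092 | 0.074 | 0.051 |
| 6 | 0.141 | 0.122 | 0.104 | 0.082 | 0.054 |
| 12 | 0.262 | 0.202 | 0.160 | 0.116 | 0.067 |
| 16 | 0.333 | 0.244 | 0.188 | 0.132 | 0.073 |

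**Chance of at least one false result in either direction**

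| k | r = 0 | r = 0.3 | r = 0.5 | r = 0.7 | r = 0.9 |
|---|---|---|---|---|---|
| 1 | 0.050 | 0.050 | 0.050 | 0.050 | 0.050 |
| 5 | 0.226 | 0.209 | 0.183 | 0.148 | 0.102 |
| 6 | 0.265 | 0.241 | 0.207 | 0.164 | 0.108 |
| 12 | 0.460 | 0.397 | 0.319 | 0.232 | 0.135 |
| 16 | 0.560 | 0.475 | 0.374 | 0.264 | 0.146 |

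Simulation agrees with the integration. For k = 16 and r = 0.7, for instance, it gives 0.132 favouring CBT and 0.264 in either direction.

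**What naming one outcome gains.** Assume 1:1 allocation, 60 per arm and no dropout. One outcome at 0.05 then has 80% power for a standardized difference of (1.960 + 0.842) × √(2/60) = 0.51. If 16 outcomes stay co-equal with Bonferroni control, the level is 0.05/16 = 0.0031 and the detectable difference rises to about 0.69.

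**The case against.** **The text is incomplete.** The front part of the protocol and the design flowchart were not available, and an outcome could be named there. That limits confidence. Still, the abstract, objectives, procedures and statistics are all available, and those are the places where a primary outcome would be expected.

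**The study may be meant as exploratory.** The objectives section speaks of exploring effects, and section 9 uses similar wording. This is plausible, but no section available declares it. The abstract says efficacy, the design is a randomized comparison with a sham control, and section 9 expects the results to help clinicians develop effective treatment strategies. The sponsor can settle this by stating which is meant.

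**There is a hint at an outcome.** The Figure 2 caption gives reduced hypervigilance as what CBT aims at, and the background describes EHAS as a validated scale. The caption describes how the therapy works and does not designate a trial outcome.

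**The figures depend on the chosen families.** This stands. The protocol does not say which scales are efficacy tests, DSI, GSS and RSI are never spelled out, and repetition of every scale at week 12 is inferred. The upper ends need zero correlation. A smaller family gives a smaller figure: two scales at r = 0.9 give 3.5%. That is still above 2.5%, so the direction of the problem does not change.

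**Conclusion.** The concern holds on the text available. The protocol states an efficacy objective, lists 14 or 15 questionnaires plus HRV without ranking them, and applies one 0.05 rule to all, so the main claim is not held at its nominal error.

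The size can only be illustrated. At a correlation of 0.5, the chance of a false result favouring CBT is about 9% to 10% for five or six symptom scales and 16% to 19% for 12 to 16 outcomes, against 2.5% for one named outcome. The smaller of these two families, even at a correlation of 0.9, roughly doubles the 2.5%. Sub-scores, several HRV indicators or subtype analyses would add to these figures.

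This must be fixed, because it concerns the trial's main claim and cannot be repaired once results have been seen by arm. Confidence is medium, because part of the protocol was not available.

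**What to change.** Amend the protocol before any outcome data are seen by arm. The sponsor chooses the instrument to match the first hypothesis. Suggested wording:

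> The primary outcome is the [instrument] score at the week-12 assessment. It will be compared between arms by [one test fixed now, for example ANCOVA adjusted for baseline score and center] at two-sided 0.05, whatever the normality test shows. Efficacy of CBT will be claimed on this outcome only. All other questionnaires and HRV indicators are secondary and will be reported as estimates with 95% confidence intervals.

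ANCOVA is an example; what matters is that one test is fixed in advance. The Project Abstract and Research Objectives should be aligned with the new wording. If the study is meant to be exploratory, or outcomes have already been seen by arm, the amendment should say so and the efficacy results should be reported as exploratory.

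The cost is one paragraph, with no change to visits or data collected. Timing matters: this is Version 8, dated 11/19/2024, of a study "with the study period ending on December 31, 2025". The downside is that a significant secondary scale could no longer support an efficacy claim, so the claim rests on the one chosen instrument.
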